### **6.3. Randomization**

Please refer to Section 6.1.

#### **6.3.1. Randomization and Study Drug Administration**

- Enter subject information in the IWRS to receive randomization assignment
- Dispense study drug as directed by the IWRS
- Instruct the subject on the packaging, storage, and administration of the study drug
- Observe the subject taking the first dose of study drug and record the time of first dose

### **6.4. Study Assessments**

#### **6.4.1. Priority of Assessments**

Subject-reported outcomes are recommended to be completed before any other study procedures. Invasive study procedures such as blood draws and biopsies should be done at the end of a study visit, as much as possible. Investigator questionnaires/assessments should be performed prior to reviewing subject-reported outcomes for that visit, as much as possible.

#### **6.4.2. Efficacy**

Efficacy assessments will be performed at the time points indicated in the Study Procedures Table ([Appendix 2](#)).

##### **6.4.2.1. Mayo Clinic Score (MCS)**

Mayo Scoring system for assessment of ulcerative colitis activity. Refer to [Appendix 4](#).

##### **6.4.2.2. 36-Item Short Form Healthy Survey**

The SF-36 is a health related quality of life instrument consisting of 36 questions belonging to 8 domains in 2 components and covers a 4-week recall period:

- Physical well-being, 4 domains: physical functioning (10 items), role physical (4 items), bodily pain (2 items), and general health perceptions (5 items)
- Mental well-being, 4 domains: vitality (4 items), social functioning (2 items), role emotional (3 items), and mental health (5 items).

The remaining item (health transition) is not part of the above domains but is kept separately. These scales will be rescaled from 0 to 100 (converting the lowest possible score to 0 and the highest possible score to 100), with higher scores indicating a better quality of life. The SF-36 is not disease specific and has been validated in numerous health states.

#### 6.4.2.3. Work Productivity and Activity Impairment Questionnaire (WPAI)

The WPAI is designed to measure the effect of general health and symptom severity on work productivity and regular activities during the past seven days.

#### 6.4.2.4. EQ-5D

The EQ-5D is a standardized instrument developed by the EuroQol Group as a measure of health-related quality of life that can be used in a wide range of health conditions and treatments.

#### 6.4.2.5. IBDQ

This disease-specific questionnaire comprises 32 questions divided into four health subscales: bowel symptoms (10 questions); systemic symptoms, including sleep disorders and fatigue (5 questions); emotional function such as depression, aggression and irritation (12 questions); and social function, meaning the ability to participate in social activities and to work (5 questions).

### 6.4.3. Safety

Safety will be assessed via AEs, concomitant medications, physical examinations (complete and symptom-driven), vital signs, ECGs, and clinical laboratory results.

#### 6.4.3.1. Clinical Laboratory Evaluations

The hematology, serum chemistry, coagulation laboratory, and stool analyses will be performed at a central laboratory. Reference ranges will be supplied by the central laboratory and will be used by the investigator to assess the laboratory data for clinical significance and pathological changes.

Blood samples will be collected by venipuncture (or optional indwelling catheter for PK sampling days) in the arm at the time points indicated in the Study Procedures Table ([Appendix 2](#)). In addition, urine samples for the clinical laboratory assessments will be collected. An overnight fast (no food or drinks, except water) of at least 8 hours will be required prior to collection of blood samples for lipid testing.

A stool sample should also be collected at any time during the study for culture for pathogenic bacteria, ova and parasites, and *C. diff* toxin assay when a subject becomes symptomatic, including worsening or return of disease activity.

Refer to [Appendix 7](#) for table of clinical laboratory tests.

Laboratory values outside the normal range will be flagged and clinical relevance will be assessed by the investigator. More frequent sampling as well as additional tests may be performed as deemed necessary by the investigator.

Note that in the case where clinically significant laboratory test results are a potential reason for discontinuation from the study drug and/or withdrawal from the study, retesting of the affected parameter(s) should be prompt (within 3 to 7 days [except creatinine, which should be retested 7 to 14 days apart]).

The details of sample handling and shipment instructions will be provided in a separate laboratory manual.

#### 6.4.3.2. Pregnancy Testing (for females of childbearing potential)

All females meeting the childbearing potential criteria must have a serum pregnancy testing at screening and an in-clinic urine pregnancy test must be completed every 4 weeks at a minimum. If any pregnancy test is positive, study drug should be immediately interrupted and the subject should have a serum pregnancy test in clinic that will be centrally reported.

#### 6.4.3.3. Vital Signs

Vital signs will be measured at the time points indicated in the Study Procedures Table ([Appendix 2](#)).

Vital signs should be taken after the subject has been resting in the seated or supine position for at least 5 minutes and will include pulse rate, respiratory rate, systolic and diastolic blood pressure, and temperature.

#### 6.4.3.4. Physical Examination

A physical examination should be performed at the time points indicated in the Study Procedures Table ([Appendix 2](#)). Any changes from screening will be recorded. Weight will be measured at all visits. Height will be measured at screening only. Subjects should be instructed to remove shoes prior to measurement of height.

At screening, a complete physical examination will be performed. A complete physical examination will include source documentation of general appearance and the following body systems: head, neck, and thyroid; eyes, ears, nose, throat, mouth and tongue; chest (excluding breasts); respiratory, cardiovascular, lymph nodes; abdomen; skin, hair, nails; musculoskeletal; and neurological. Symptom-driven physical examinations will be performed at all other visits based on reported signs and symptoms.

#### 6.4.3.5. 12-lead Electrocardiogram

A resting 12-lead ECG will be performed at the time points indicated in the Study Procedures Table ([Appendix 2](#)).

The ECG should be obtained after the subject has been resting in the supine position for at least 5 minutes and will include heart rate (HR), inter-beat (RR), QRS, uncorrected QT, morphology, and rhythm analysis. Electrocardiograms will be interpreted by the investigator (or qualified designee) for clinical significance and results will be entered into the eCRF.

#### 6.4.4. Pharmacokinetics Assessments

The PK sample at Week 4 is collected post-dose (at least 30 minutes and up to 3 hours after study drug dosing). For this visit, it is preferred that study drug dosing is done in clinic. The PK sample at Weeks 26 can be collected at any time without regard to dosing. The PK sample at Weeks 10 and 58 are collected at pre-dose (within 2 hours prior to dosing).

Subjects who consent to the optional PK substudy will have additional plasma PK samples at any single visit from Week 2 to Week 10, collected pre-dose, and at 0.5, 1, 2, 3, 4 and 6 hours after supervised dosing in the clinic. If a sub-study PK sample is scheduled to be collected at the same time as a sparse PK sample, only one sample should be collected.

For all visits with PK sampling, the time of dose taken prior to and on the day of visit will be noted in the eCRF. Plasma concentrations of filgotinib and its metabolite (GS-829845) will be analyzed.

#### 6.4.5. Biomarker Assessments

Blood samples will be collected on Day 1 and at Weeks 4, 10, 26, and 58.

Blood samples may be analyzed for assessment of markers of inflammation, immune status, and JAK-STAT pathway activation.

CCI

[REDACTED]

[REDACTED]

[REDACTED]

#### 6.5. Post-Treatment Assessments

All subjects must complete the PTx assessments 30 days after the last dose of study drug. Subjects who enter into the LTE study (GS-US-418-3899) will not complete PTx assessments associated with this protocol.

The following will be performed and documented:

- Symptom directed PE
- Obtain body weight and vital signs (resting blood pressure, respiratory rate, pulse and temperature)
- Review AEs and concomitant medications

- Obtain blood samples (reference Study Procedure Table in [Appendix 2](#))
- Obtain urine sample (reference Study Procedures Table [[Appendix 2](#)])
  - Pregnancy test (for females of child bearing potential only)

#### **6.6. Early Termination Assessments**

The following will be performed and documented:

- Symptom directed PE
- Obtain body weight and vital signs (resting blood pressure, respiratory rate, pulse and temperature)
- Perform 12-Lead ECG (for subjects who terminate prior to Week 10)
- Review AEs and concomitant medications
- Collect e-Diary back from subject
- Collect the variables to calculate partial MCS (see [Appendix 4](#))
  - Site collects patient assessments at each visit
  - MCS calculated centrally after all components have been captured electronically
- Obtain fasting blood samples (reference Study Procedure Table in [Appendix 2](#))
- Obtain urine sample (reference Study Procedures Table [[Appendix 2](#)])
  - Pregnancy test (for females of child bearing potential only)

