**Concomitant Ulcerative Colitis Medication Management:**

Subjects on permitted concomitant medications for UC that are described in the inclusion criteria (eg, 5-ASA, and immunomodulators) must remain on stable doses until Week 10. Steroids must remain stable to Week 14.

Starting at Week 14, subjects who are on concomitant steroids must begin tapering steroid therapy. The dose should be reduced at a rate starting at 2.5 mg per week up to 5 mg per week (or equivalent taper if not prednisone). Subjects who are on budesonide should have their daily dose reduced by 3 mg every 3 weeks until they are completely off steroids. For subjects undergoing taper, steroids may be increased or restarted at doses up to and including their baseline dose if return of symptoms is apparent. These subjects will not be considered treatment failures. Subjects who need to restart or increase steroid treatment at a dose that exceeds their baseline dose of steroids (dose may not exceed 30 mg prednisone [or equivalent] or budesonide 9 mg/day) will be considered treatment failures for all clinical endpoints but will be permitted to remain in the study.

For additional prohibited UC medications, reference [Table 5-1](#).

---

Test Product, Dose, and Mode of Administration:	Filgotinib 200 mg oral tablet, once daily Filgotinib 100 mg oral tablet, once daily
Reference Therapy, Dose, and Mode of Administration:	PTM filgotinib 200 mg oral tablet, once daily PTM filgotinib 100 mg oral tablet, once daily

---

---

**Criteria for  
Evaluation:**

- Safety:** Assessment of AEs and concomitant medications will continue throughout the duration of the study. Safety evaluations include documentation of AEs, PE (complete or symptom driven), vital signs, and clinical laboratory evaluations (hematology, chemistry, urinalysis). An ECG will be performed at screening, Week 10 (or at Early Termination (ET) if subject terminates prior to Week 10), Week 26 and Week 58.

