Week		0	2	4	6	10	11	14	17	20	23	26	30	34	38	42	46	50	54	58			
Study Day	-30 to -1	1	15	29	43	71	78	99	120	141	162	183	211	239	267	295	323	351	379	407			
Visit Window			±3	±3	±3	±2	±3	±5	±5	±5	±5	±5	±5	±5	±5	±5	±5	±5	±5	±3	±3		
Urine drug screen i	X																						
Urinalysis	X	X				X														X			
Pregnancy Test j	X	X		X	X	X		X	X	X	X	X	X	X	X	X	X	X	X	X	X	X	
TB k	X																						
Chest x-ray l	X																						
HBV, HCV, HIV screening m	X																						
HBV DNA monitoring (Japan) n				X	X	X		X	X	X	X	X	X	X	X	X	X	X	X	X	X		
HBV monitoring (other regions) n						X				X				X				X		X			
Hematology	X	X	X	X	X	X		X		X		X		X		X		X		X	X	X	
Chemistry	X	X	X	X	X	X		X		X		X		X		X		X		X	X	X	
Lipid profile (fasting) o		X				X						X								X		X	
CRP	X	X	X	X	X	X		X		X		X		X		X		X		X	X	X	
Serum immunoglobulin		X		X		X						X								X	X	X	
Blood TCR/BCR repertoire samples p		X		X		X						X								X			
Plasma biomarker sample		X		X		X						X								X			

[figure not shown]

Period	Screen	Treatment																				Follow-up		
		2	3	4	5	6	7	8	9	10	11	12	13	14	15	16	17	18	19	20	PTx a	ET		
Visit	1																							
Week		0	2	4	6	10	11	14	17	20	23	26	30	34	38	42	46	50	54	58				
Study Day	-30 to -1	1	15	29	43	71	78	99	120	141	162	183	211	239	267	295	323	351	379	407				
Visit Window			±3	±3	±3	±2	±3	±5	±5	±5	±5	±5	±5	±5	±5	±5	±5	±5	±5	±3	±3			
Serum biomarker sample		X		X		X						X								X				
Blood transcriptome sample		X		X		X						X								X				
PK collection (sparse) g				X		X						X								X				
vfPBMC c		X		X		X						X								X				
PK substudy d				X																				
CCI																								
HRQoL Surveys a		X				X						X								X				
HCRU questionnaire		X	X	X	X	X	X	X		X		X		X		X		X		X				

- a The Post Treatment (PTx) visit should occur 30 days after the last dose of study drug. Only subjects who roll over into the LTE study (GS-US-418-3899) will not complete PTx assessments.
- b For subjects who terminate prior to Week 10
- c A complete physical examination (PE) including, vital signs, body weight, and height will be performed at screening. (GU exam at investigator discretion). A symptom directed PE may be done as needed at other time points.

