Week 2	Week 2	15	2	22
Week 4	Week 4	29	23	36
Week 6	Week 6	43	37	57
Week 10	Week 10	71	58	For subjects who entered Maintenance Study: minimum of 85 and Study Day of [Maintenance first dose date]; for other subjects: ≥ 71

Note: ECG, lipid profile, fecal lactoferrin, and fecal calprotectin are collected postbaseline at Weeks 10, 26, and 58 only and the corresponding analysis windows will be applied; serum immunoglobulin is collected postbaseline at Weeks 4, 10, 26, and 58 only and the corresponding analysis windows will be applied.

Table 3-8. Analysis Visit Windows for Maintenance Study Weight, Vital Signs, ECG, Hematology, Chemistry, Lipid Profile, Serum Immunoglobulin, hs-CRP, Fecal Calprotectin and Fecal Lactoferrin

Nominal Visit	Analysis Visit	Nominal Day (M-Day)	Lower Limit (M-Day)	Upper Limit (M-Day)
Week 10/11	Re-Baseline	1	none	1
Week 14	Maintenance Week 3	22	2	43
Week 20	Maintenance Week 9	64	44	85
Week 26	Maintenance Week 15	106	86	134
Week 34	Maintenance Week 23	162	135	190
Week 42	Maintenance Week 31	218	191	246
Week 50	Maintenance Week 39	274	247	302
Week 58	Maintenance Week 47	330	303	≥ 330

Note: ECG, lipid profile, fecal lactoferrin and fecal calprotectin are collected postbaseline at Weeks 10, 26, and 58 only and the corresponding analysis windows will be applied; serum immunoglobulin is collected postbaseline at Weeks 4, 10, 26, and 58 only and the corresponding analysis windows will be applied.

3.8.3. Selection of Data in the Event of Multiple Records in an Analysis Visit Window

Depending on the statistical analysis method, single values may be required for each analysis window. For example, change from baseline by visit usually requires a single value, whereas a time-to-event analysis would not require 1 value per analysis window.

If multiple, valid, nonmissing, continuous measurements exist in an analysis window, records will be chosen based on the following rules if a single value is needed:

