7.5. Electrocardiogram Results

A shift table of the investigators' assessment of ECG results at each visit compared with baseline (or re-baseline) values will be presented by treatment group for each Induction Study, Cohort A and B Induction Studies Combined, and Maintenance Study using the following categories: normal; abnormal, not clinically significant; abnormal, clinically significant. The number and percentage of subjects in each cross-classification group of the shift table will be presented. Subjects with a missing value at baseline (or re-baseline) or postbaseline will not be included in the denominator for percentage calculation.

No formal statistical testing is planned.

A by-subject listing for ECG assessment results will be provided by subject ID number and time point in chronological order.

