Fecal Lactoferrin, Calprotectin	X					X						X									X	
Urine drug screen ⁱ	X																					
Urinalysis	X	X				X															X	
Pregnancy Test ^j	X	X		X	X	X		X	X	X	X	X	X	X	X	X	X	X	X	X	X	X
TB ^k	X																					
Chest x-ray ^l	X																					
HBV, HCV, HIV screening ^m	X																					
HBV DNA monitoring (Japan) ⁿ				X	X	X		X	X	X	X	X	X	X	X	X	X	X	X	X	X	X
HBV monitoring (other regions) ⁿ						X				X				X				X			X	
Hematology	X	X	X	X	X	X		X		X		X		X		X		X		X	X	X
Chemistry	X	X	X	X	X	X		X		X		X		X		X		X		X	X	X
Lipid profile (fasting) ^o		X				X						X									X	X
CRP	X	X	X	X	X	X		X		X		X		X		X		X		X	X	X
Serum immunoglobulin		X		X		X						X									X	X

Period	Screen	Treatment																			Follow-up	
Visit	1	2	3	4	5	6	7	8	9	10	11	12	13	14	15	16	17	18	19	20	PTx ^a	ET
Week		0	2	4	6	10	11	14	17	20	23	26	30	34	38	42	46	50	54	58		
Study Day	-30 to -1	1	15	29	43	71	78	99	120	141	162	183	211	239	267	295	323	351	379	407		
Visit Window			±3	±3	±3	±2	±3	±5	±5	±5	±5	±5	±5	±5	±5	±5	±5	±5	±5	±5	±3	
Blood TCR/BCR repertoire samples ^p		X		X		X					X									X		
Plasma biomarker sample		X		X		X					X									X		
Serum biomarker sample		X		X		X					X									X		
Blood transcriptome sample		X		X		X					X									X		
PK collection (sparse) ^q				X		X					X									X		
vPBMC ^r		X		X		X					X									X		
PK substudy ^s				X																		
CCI																						
HRQoL Surveys ^u		X				X					X									X		
HCRU questionnaire		X	X	X	X	X	X	X		X		X		X		X		X		X		

- a The Post Treatment (PTx) visit should occur 30 days after the last dose of study drug. Only subjects who roll over into the LTE study (GS US 418 3899) will not complete PTx assessments.
- b For subjects who terminate prior to Week 10
- c A complete physical examination (PE) including, vital signs, body weight, and height will be performed at screening. (GU exam at investigator discretion). A symptom directed PE may be done as needed at other time points.
- d Diary data and other eligibility criteria should be reviewed prior to scheduling endoscopy. Perform the screening colonoscopy/flexible sigmoidoscopy within 2 weeks of Day 1 (Day 14 to -1). Subject should meet stool frequency and rectal bleeding requirements based on diary data prior to endoscopy performance.

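### The notes to SAP Tables 3-7 and 3-8 overlook the early-termination ECG and lipid panel, so an ECG or LDL/HDL value taken at early termination before Study Day 58 enters no summary table

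*Protocol*

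**What the plan says.** **What is collected.** Protocol 6.6 lists among the ET procedures "Perform 12-Lead ECG (for subjects who terminate prior to Week 10" and "Obtain fasting blood samples (reference Study Procedure Table in" Appendix 2. The protocol synopsis, under Criteria for Evaluation (Safety), treats the ET tracing as a stand-in for the Week 10 one. After screening, it places ECGs at "Week 10 (or at Early Termination (ET) if subject terminates prior to Week 10), Week 26 and Week 58". In protocol Appendix 2 the row "Lipid profile (fasting") carries a mark in the ET column with no restriction to termination before Week 10. SAP Appendix 1 reproduces that schedule. Its ECG row has an ET mark with the footnote "For subjects who terminate prior to Week 10", and its lipid row also has an ET mark.

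**What the SAP assumes for analysis.** The note under SAP Table 3-7 says "ECG, lipid profile, fecal lactoferrin, and fecal calprotectin are collected postbaseline at Weeks 10, 26, and 58 only" and that the matching windows apply. The note under Table 3-8 says the same. The windows relevant to ECG and lipids are then:

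- Induction Week 10: from Study Day 58, with no effective upper limit for subjects who do not enter Maintenance.
- Maintenance, nominal Week 26: M-Days 86 to 134.
- Maintenance, nominal Week 58: from M-Day 303, open-ended.

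**What is tabulated.** SAP 7.5 plans one ECG summary, in which the investigators' "assessment of ECG results at each visit compared with baseline (or re-baseline) values will be presented by treatment group". Subjects with no baseline or post-baseline value are left out of its denominator, and all ECG results are listed by subject. For LDL and HDL, SAP 7.2.1 gives descriptive statistics by time point. SAP 7.2.4 gives shifts in NCEP categories at Week 10 for Induction and at Weeks 26 and 58 for Maintenance.

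**The concern.** The SAP's note conflicts with the protocol and with the SAP's own schedule. The protocol requires an ECG from a subject who stops before Week 10 so that such a subject has a post-baseline tracing. The window rules then give that tracing no analysis visit unless it was taken on or after Day 58. Because the ECG table is by visit and drops subjects without a value, it describes only subjects who stayed to about Day 58 or later. The same happens to LDL and HDL taken at ET. The protocol's risk/benefit section (1.4) names lipid effects as a potential benefit, so these are not incidental tests.

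What is at stake is the completeness of two safety displays. No primary or key secondary efficacy result is affected.

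**Working it through.** The plan gives no figure to reproduce. The check maps each possible ET day to the windows, keeping only the Week 10, 26 and 58 rows as the notes direct.

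**Inputs**

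- Nominal Week 10 day: Study Day 71. Week 10 window lower limit: Day 58 (SAP Table 3-7).
- Nominal Week 58 day: M-Day 330. Windows: M-Days 86 to 134, and from 303 (SAP Table 3-8).
- An ET ECG is required only for termination before Week 10; ET lipids are required at any ET (protocol 6.6 and Appendix 2; SAP Appendix 1).

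**Induction (ECG and LDL/HDL)**

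- Post-baseline days before nominal Week 10: Days 2 to 70, so 70 − 2 + 1 = 69 days.
- In no window: Days 2 to 57, so 57 − 2 + 1 = 56 days.
- Taken as Week 10: Days 58 to 70, so 70 − 58 + 1 = 13 days.
- Share in no window: 56 / 69 = 81%.

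**Maintenance (LDL/HDL only, since no ET ECG is scheduled after Week 10)**

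- Days before nominal Week 58: M-Days 2 to 329, so 329 − 2 + 1 = 328 days.
- In no window: M-Days 2 to 85 (84 days) plus 135 to 302 (168 days), so 84 + 168 = 252 days.
- In a window: M-Days 86 to 134 (49 days) plus 303 to 329 (27 days), so 49 + 27 = 76 days. Check: 252 + 76 = 328.
- Share in no window: 252 / 328 = 77%.

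These are shares of calendar days. The documents give neither a dropout rate nor a distribution of stopping times, so they do not convert to a number of subjects.

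**Where each ET result goes**

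| ET result | Summary table | Listing |
|---|---|---|
| ECG, Days 2 to 57 | none | yes |
| ECG, Day 58 onward (termination before Week 10) | Week 10 shift | yes |
| LDL/HDL, Days 2 to 57 | none | yes |
| LDL/HDL, M-Days 2 to 85 or 135 to 302 | none | yes |
| LDL/HDL, M-Days 86 to 134 or from 303 | Week 26 or Week 58 | yes |
| Total cholesterol, triglycerides, any ET day | CTCAE-graded abnormalities, any post-baseline time (SAP 7.2.2) | yes |

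**How the SAP handles comparable cases.** Graded laboratory abnormalities use any post-baseline time point (SAP 7.2.2.1). The individual liver tests and the blood-count tables use the worst post-baseline value (SAP 7.2.3). For quality-of-life measures in Maintenance, Table 3-6 uses two adjoining windows that cover M-Days 2 to 358 without a gap. ECG, LDL and HDL have neither arrangement.

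**The case against.** The strongest reply is that the clinically important cases are caught elsewhere. Under protocol 7.5, an abnormal ECG with signs or symptoms that meets the adverse event definition must be reported as one. A laboratory abnormality that leads to stopping study drug must be reported too, unless it reflects the underlying condition. SAP 7.1.5.1 counts any adverse event leading to premature discontinuation as treatment-emergent, and SAP 7.1.6.1 tabulates those events by arm. Graded lipids count at any time. This stands, and it limits the gap to ECG abnormalities not reported as adverse events and to LDL and HDL values at ET.

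It could also be said that SAP 7.5 covers each visit, and that ET is a visit. Nothing in SAP 3.8.2 defines an ET analysis visit, however, and the notes say the data exist only at the three scheduled weeks. At best the text is ambiguous.

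Four stronger readings are tempting, and the documents do not support them.

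- **A reader might infer that everyone who stops early leaves these summaries.** ET values from Day 58 count as Week 10, and some Maintenance ET lipids fall in a window. Subjects who stop in Maintenance stay in the summaries for visits they attended. Their lack of an ET ECG comes from the protocol schedule, not from the SAP note.
- **A reader might infer that the SAP 7.7 statement of no deviations from the protocol's safety analyses is false.** Protocol 8.3 excludes subjects with missing laboratory results from that time point's statistics. Protocol 8.6.3 summarises laboratory data at scheduled time points. Protocol 8.6.4 asks for ECG listings and for summaries as appropriate. A by-visit shift plus a listing breaks no explicit commitment.
- **A reader might multiply the 81% by an assumed dropout rate to count lost ECGs.** Both the rate and the timing would be invented.
- **A reader might go on to ask for a corrected QT analysis, because protocol 6.4.3.5 says the ECG** "will include heart rate (HR), inter-beat (RR), QRS, uncorrected QT, morphology, and rhythm analysis". Protocol 1.2.2.2 describes only a slight, non-adverse heart-rate increase with the metabolite at 8-fold the clinical peak exposure, and reports no relevant ECG or QT effect. Nor does the protocol say that individual QT and RR values are database fields.

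**Conclusion.** The contradiction is real and the consequence is narrow. The notes to SAP Tables 3-7 and 3-8 misstate when ECG and lipids are collected. As written, an ET ECG or LDL/HDL value on Days 2 to 57, and an ET LDL/HDL value on M-Days 2 to 85 or 135 to 302, enters no summary table. The ECG shift table is thereby restricted to subjects with a tracing from about Day 58 onward.

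This conclusion rests on reading the notes literally, with no unwritten ET visit in the programming. It does not rest on any assumption about how many subjects stop early. That those who stop early have more abnormal tracings is plausible, but the documents do not show it. Severity is minor: the data are still listed, reported adverse events and graded lipids are still tabulated, and efficacy is untouched.

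**What to change.** 1. In the notes to SAP Tables 3-7 and 3-8, add ET to the collection times: ECG for termination before Week 10, and lipid profile at any ET.
2. In SAP 7.5, add by arm a shift from baseline (or re-baseline) to the worst post-baseline on-treatment ECG, using the three existing categories and all tracings, including ET and unscheduled ones.
3. In SAP 7.2.4, add by arm a last on-treatment shift for LDL and HDL in the existing NCEP categories, including ET values.
4. State what on-treatment means for items 2 and 3, since an ET visit can follow the last dose. The data cut-offs already set out in SAP 7.2 for laboratory results (up to 30 days after the last dose, or the first Maintenance dose) would serve.

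The cost is a wording correction and a few extra tables from ECG assessments and lipid results already collected, with no added visits or procedures. If the SAP is already final, its introduction provides for documenting the change in the clinical study report.
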